**Objective**

The primary objective of the proposed study is to evaluate the safety and efficacy of Brexpiprazole in adults with borderline personality disorder (BPD). Eighty subjects with BPD will be randomized in a 1:1 fashion to either Brexpiprazole (starting at 1mg/day for one week and going to 2mg in a fixed dose fashion after 1 week) or matching placebo for 12 weeks of active treatment. The hypothesis to be tested is that Brexpiprazole will result in greater rates of reduction in symptoms of BPD compared to placebo (improvement in symptoms will be indicated by lower scores on established outcome measures of BPD symptoms that have been used in prior studies).

**Background of BPD**

Borderline personality disorder is characterized by mood instability, cognitive symptoms, impulsive behavior, and disturbed relationships (1–3). A variety of psychotherapies have been developed (4–6) and, while research on the use of medication is ongoing, no drug has been approved in the United States or elsewhere for its treatment (7). Second generation antipsychotics have been the most intensively studied (8–11). Current treatments for BPD are often inadequate. Dialectical behavioral therapy has been shown to reduce BPD but finding trained psychologists is difficult.

**Choice of Medication**

One illness that is difficult to treat is borderline personality disorder (12–17), which is characterized by a pervasive pattern of severe psychopathological symptoms with instability of

affect regulation, impulse control, and aggression (18-24). Dysfunctions in the serotonergic and dopaminergic systems have been demonstrated in—and considered as possible causes for—symptoms associated with the disorder (25-28). Several studies on the use of traditional (29) and atypical antipsychotic agents in patients with borderline personality disorder (30–31) have shown a positive effect on individual symptoms (29, 32–36). However, we are not aware of any study evaluating Brexpiprazole in the treatment of patients with borderline personality disorder. In the proposed double-blind, placebo-controlled study, the influence of Brexpiprazole on the multifaceted psychopathological symptoms and aggression of patients with borderline personality disorder will be investigated.

Brexpiprazole therefore has distinctive properties that make it a promising option for patients with BPD. Brexpiprazole is a novel D2 partial agonist, has affinity for 5-HT1A, acts as an antagonist of the noradrenergic  $\alpha$ 1/2 receptor, partial agonist for D3, and antagonist for 5-HT2A (37-39). In addition, because of low rates of side effects, Brexpiprazole should be a well-tolerated and in fact desired medication approach to BPD.

The aim of the present study is to examine the efficacy and safety of Brexpiprazole vs. placebo in adults with BPD, as indicated by a score of at least 9 on the Zanarini Rating Scale for Borderline Personality Disorder (“Zanarini scale”), a scale of illness severity, at the baseline visit.

### **Study Design/Methodology**

Eighty individuals with a prior diagnosis of BPD will be recruited for a double-blind, placebo-controlled pilot study in which Brexpiprazole or placebo is administered in a 1:1 fashion. All 80 subjects will have current BPD per DSM-5 criteria. Following baseline measures, subjects will receive Brexpiprazole (1mg/day for one week and then 2mg/day thereafter) or inactive placebo. Participants will be seen every week for the first 2 weeks and then every 2 weeks after that. At week 12, subjects will start a 1-week taper off the medication. Efficacy and safety measures will be performed at each visit.

### **Study Population/Sample Size**

80 male and female outpatients aged 18-65 with a current primary diagnosis of BPD.

### **Subjects**

#### *Inclusion criteria:*

- 1) Men and women age 18-65;
- 2) Primary diagnosis of BPD
- 3) Zanarini scale score of at least 9 at baseline
- 4) Ability to understand and sign the consent form.

#### *Exclusion criteria:*

- 1) Unstable medical illness based on history or clinically significant abnormalities on baseline physical examination
- 2) Subjects with schizophrenia or bipolar I disorder
- 3) Subjects with an active substance use disorder
- 4) Current pregnancy or lactation, or inadequate contraception in women of childbearing potential
- 5) Subjects considered an immediate suicide risk based on the Columbia Suicide Severity rating Scale (C-SSRS) ([www.cssrs.columbia.edu/docs](http://www.cssrs.columbia.edu/docs))

- 6) Illegal substance use based on urine toxicology screening (excluding marijuana given the high rates of marijuana use in BPD and the lack of interaction with brexpiprazole).
- 7) Initiation of psychological interventions within 3 months of screening
- 8) Use of any new psychotropic medication started within the last 3 months prior to study initiation
- 9) Previous treatment with Brexpiprazole
- 10) Cognitive impairment that interferes with the capacity to understand and self-administer medication or provide written informed consent

Advertisements will target this study population. Interested individuals will be asked to contact a study coordinator or complete an online survey expressing interest. Individuals will then undergo a phone screen before being scheduled for a first appointment. After being screened, potential subjects will be scheduled for a first appointment in which we will confirm medical and psychiatric history, laboratory tests, and inclusion/exclusion criteria.

### **Drugs, Dosages, and Regimens**

All subjects who are randomized to Brexpiprazole will receive 1mg/day during the first week of the study, and then 2mg/day for the remainder of the study. Dosage changes and reductions will not be permitted. After study conclusion, the dose will be tapered off during a 1-week follow-up period.

### **Randomization**

Participants are randomized (1:1) to receive placebo or brexpiprazole by the investigational pharmacy at the University of Chicago. The study blind will be maintained by over-encapsulation, making placebo and active treatments appear identical in size, weight, shape, and color. Dosage changes and reductions will not be permitted during the study and participants will be discontinued if they experienced intolerance.

### **Blinding**

Blinding is critical to the integrity of this clinical study. However, in the event of a medical emergency or pregnancy in an individual subject, in which knowledge of the investigational product is critical to the subject's management, the blind for that patient may be broken by the treating physician.

### **Treatment Duration, Visit Frequency, and Procedures**

This is a 13-week study (12 weeks of acute treatment followed by a 1-week tapering phase). Subjects will be seen at baseline and then every week for the first 2-4 weeks and then every two weeks after that.

#### *Assessments at each visit*

Those subjects who appear appropriate for the study, based on telephone screening, will be invited for a baseline assessment. The duration of the baseline assessment will be approximately 90 minutes and will include the following: Informed consent, Demographic data, Concomitant medications (no psychotropic medications will be allowed), Family history data, Medical evaluation including physical examination, EKG, weight, and vital signs, Urine pregnancy test (for women of childbearing years) and urine drug screen, and a psychiatric evaluation (using the following measures: MINI International Neuropsychiatric Interview (40); Depressive symptoms will be rated with the 24-item Hamilton Depression Rating Scale (HAM-D) (41); Anxiety

symptoms will be assessed using the Hamilton Anxiety Rating Scale (HAM-A) (42); Psychosocial functioning will be evaluated using the patient-rated version of the Sheehan Disability Scale (SDS) (43); Quality of Life Inventory (QOLI) (44); The Cambridge-Chicago Compulsivity Trait Scale (CHI-T); and the Columbia Suicide Severity Rating Scale (C-SSRS)). During the consent process, individuals will be given time to review the consent form and given the opportunity to ask any questions that may arise before signing the informed consent form. Throughout the study, subjects will be asked questions about the study to ensure that they continue understanding study procedures. Blood samples will be collected at both baseline and last visits to measure blood sugar, glutathione, and cholesterol levels. All follow-up visits will include safety measures (adverse events, vital signs, C-SSRS), weight, BPD measures, and other psychiatric measures.

Due to the pandemic of COVID19, study participants can perform their baseline and follow-up visits online using encrypted Zoom instead of in person visits. All inventories will be assessed. Blood samples and urine toxicology, however, will be at the discretion of the study PI. In cases where they are considered medically necessary, the participant can have them drawn locally and submitted to the study team.

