### *Safety Assessments*

Safety and tolerability will be assessed using spontaneously reported adverse events data, C-SSRS, vital signs, and by evaluating premature termination. Safety assessments (sitting blood pressure, heart rate, adverse effects, and concomitant medications) will be documented at each visit. Subjects who are an immediate suicide risk will be removed from the study and appropriate clinical intervention (e.g. hospitalization) will be arranged. Study team members are mandated reporters and as such, will arrange for the subject to be taken to the emergency room if any intent to harm themselves is expressed. Urine pregnancy tests will be performed at the initial visit. Subjects who have a positive urine pregnancy test will be excluded from the study. Assessment of side effects will be done at each visit.

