### *Risks of Brexpiprazole*

The most common side effects associated with Brexpiprazole include:

- Weight gain
- Inner sense of restlessness (feeling like one needs to move)

Brexpiprazole may cause more serious side effects including:

- Stroke in elderly people
- Neuroleptic Malignant Syndrome (high fever, stiff muscles, sweating, changes in pulse, heart rate and blood pressure)
- Tardive dyskinesia (uncontrollable body movements)
- High blood sugar
- Low white blood cell count
- Decreased blood pressure
- Seizures
- Problems controlling your body temperature so that the individual feel too warm
- Difficulty swallowing that can cause food or liquid to get into the lungs

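### Low white cell count is listed as a serious risk, but no named blood test measures it, so asymptomatic cases would be missed and the rate by arm cannot be estimated

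*Combined protocol and SAP*

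**What the plan says.** The Objective section makes safety, alongside efficacy, the primary aim. The section Risks of Brexpiprazole opens its second list with "Brexpiprazole may cause more serious side effects including", and that list contains "Low white blood cell count".

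The section Assessments at each visit specifies the bloods: "Blood samples will be collected at both baseline and last visits to measure blood sugar, glutathione, and cholesterol levels". For later visits it adds: "All follow-up visits will include safety measures (adverse events, vital signs, C-SSRS), weight, BPD measures, and other psychiatric measures". The same section allows baseline and follow-up visits to be held online. Blood samples are then left to the principal investigator's discretion, with a local draw possible where judged medically necessary.

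Safety Assessments bases the safety evaluation on spontaneously reported adverse events, the C-SSRS, vital signs and premature termination. The closing paragraph under Exclusion criteria mentions laboratory tests at the first appointment without saying which. No section names a blood count.

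**The concern.** A low white cell count is a laboratory finding. Until it causes illness, none of the four methods in Safety Assessments will show it. The monitoring committee cannot review a value that nobody has measured.

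The plan's own practice makes the gap visible. Two entries in its list of more serious effects are defined by a laboratory value: high blood sugar and low white cell count. It tests the first and not the second.

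What is at stake is how the safety result can be read. If the final report recorded no low white counts, the reader could not tell whether the drug caused none or whether none was looked for. An affected participant without symptoms would also go unrecognised.

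**Working it through.** **Step 1. Set the listed risk against the planned measurements.**

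| Planned source (section) | Could it show a low white cell count? |
|---|---|
| Blood sugar, glutathione, cholesterol at baseline and last visit (Assessments at each visit) | No; none is a cell count |
| Vital signs, C-SSRS (Assessments at each visit; Safety Assessments) | No |
| Spontaneously reported adverse events (Safety Assessments) | Only if the participant has symptoms or is tested elsewhere |
| Premature termination (Safety Assessments) | Only indirectly, after symptoms |
| Unspecified laboratory tests at the first appointment (Exclusion criteria) | Unknown; at best a pre-treatment value |

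Even if the unspecified first-appointment tests included a count, there would be no on-treatment value to compare with it. The number of named on-treatment tests for this risk is zero. For asymptomatic cases there is therefore no numerator, no denominator and no rate in either arm.

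**Step 2. What a count would add.** The plan gives no figure of its own to reproduce here. It states no incidence for this effect, and its 40 per arm was set for the efficacy endpoint. The useful calculation is the upper limit on the true rate if counts were done and no case was found.

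Inputs: n = 40 on active drug (Sample Size section). Smaller values of n are assumptions that allow for online visits without a blood draw.

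Formula: with zero cases in n sampled participants, the exact one-sided 95% upper limit p solves (1 − p)^n = 0.05, so p = 1 − 0.05^(1/n).

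| Treated participants sampled | Upper limit after zero cases |
|---|---|
| 40 | 1 − 0.05^(1/40) = 1 − 0.928 = 7.2% |
| 30 | 1 − 0.05^(1/30) = 1 − 0.905 = 9.5% |
| 20 | 1 − 0.05^(1/20) = 1 − 0.861 = 13.9% |
| 10 | 1 − 0.05^(1/10) = 1 − 0.741 = 25.9% |
| 0 (tests as now named) | no limit can be given |

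The limit depends heavily on how many are sampled, so the number with a sample has to be reported next to the result.

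**The case against.** The strongest reply has four parts.

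**Symptomatic cases are not lost.** Adverse events are collected at every visit and the principal investigator must deal with safety issues as they arise. This stands. It confines the point to asymptomatic cases and to estimation of the rate.

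**The risk list is general and does not commit the plan to a test for each entry.** It includes stroke in elderly people, although enrolment stops at 65. This is fair as a general statement, but a low count differs from most of the list because it is defined by a laboratory value, and the plan does draw blood for the comparable entry, blood sugar.

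**A count at two time points helps little.** It would miss a fall that recovered before the last visit, it would not give early warning, and it leaves rates below about 7% open. All of this stands and limits what the fix can claim.

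**The first-appointment laboratory tests may include a count.** Possibly, but their content is not given and they precede treatment.

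A reader might also infer three stronger things that the documents do not support.

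- *That decreased blood pressure goes unseen as well.* The list does include "Decreased blood pressure", but the plan measures it: "Safety assessments (sitting blood pressure, heart rate, adverse effects, and concomitant medications) will be documented at each visit". A sitting reading could miss a fall confined to standing, yet the documents never call this risk postural. A standing reading is an option and its absence is not a defect.
- *That an unseen case is likely.* For assumed incidences of 0.5%, 1%, 2% and 5%, 1 − (1 − r)^40 gives 18%, 33%, 55% and 87%. Those are chances that at least one case occurs. They are not chances that one goes unseen, and no rate in the documents supports any of them.
- *That glutathione is unused and could be traded for the count.* Cholesterol is equally absent from the objective, safety and analysis sections, and no assay costs are given.

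**Conclusion.** The point holds for white cells and in a limited form. The protocol names low white cell count as a serious effect and makes safety a primary aim, but names no test that would show it during treatment. An asymptomatic case would go undetected and the rate by arm could not be estimated.

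The conclusion rests on the document text alone: no named count, and no stated content for the first-appointment tests. Its numerical size cannot be given, because the documents state no incidence. What can be sized is the benefit of measuring. The result moves from no upper limit at all to one of about 7% with all 40 treated participants sampled, or about 14% with an assumed 20. Those limits assume zero cases and describe only counts that are low when sampled. The efficacy analysis is unaffected.

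**What to change.** Add a white cell count with differential to the baseline and last-visit draws in Assessments at each visit, and bring that section into line with Safety Assessments and Risks of Brexpiprazole. In Data Analysis, state that change from baseline and the number of low values, with the threshold fixed in advance, will be tabulated by arm. Report how many participants in each arm had a baseline sample, a last-visit sample and both, since online visits make bloods discretionary. Say which visit counts as the last one, because the study continues through a one-week taper after week 12. Acknowledge in the report that two time points cannot exclude a transient fall.

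The cost is one further laboratory line on draws already planned, a short amendment, and a few incidental abnormal values to follow up. No existing assay needs to be dropped.

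### A baseline held on Zoom has no stated route for the required physical examination or the only planned pregnancy test, and nothing says that a missing result holds back randomisation or drug

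*Combined protocol and SAP*

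**What the plan says.** All references are to the combined protocol and SAP.

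- *Assessments at each visit* lists the baseline procedures. They include "Medical evaluation including physical examination, EKG, weight, and vital signs" and "Urine pregnancy test (for women of childbearing years) and urine drug screen". Bloods are separate: "Blood samples will be collected at both baseline and last visits".
- The last paragraph of that section allows remote visits during the pandemic: "study participants can perform their baseline and follow-up visits online using encrypted Zoom instead of in person visits". It keeps every inventory. It then adds: "Blood samples and urine toxicology, however, will be at the discretion of the study PI". The only local option follows directly: "In cases where they are considered medically necessary, the participant can have them drawn locally and submitted to the study team".
- *Exclusion criteria* makes an important abnormality at the baseline examination a reason to exclude (criterion 1, which can also be met on history). Current pregnancy is another (criterion 4). Of the first appointment it says "we will confirm medical and psychiatric history, laboratory tests, and inclusion/exclusion criteria".
- *Safety Assessments* plans urine pregnancy testing at the initial visit only, and excludes anyone who tests positive.
- *Study Design/Methodology* places the start of drug after the baseline measures.
- *Randomization* says: "Participants are randomized (1:1) to receive placebo or brexpiprazole by the investigational pharmacy at the University of Chicago". It does not mention results that must be in hand first.

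**The concern.** The plan permits a visit format in which one of its own required eligibility checks cannot be carried out, and in which another is not provided for. It does not say what staff should do then. A coordinator running a Zoom baseline exactly as allowed would complete the inventories, ask the investigator about bloods and toxicology, and find no instruction on the examination or the pregnancy test.

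What is at stake is participant safety rather than the efficacy analysis. A woman with an unrecognised pregnancy, or a participant with a problem visible only on examination, could be randomised and dosed. No later pregnancy test is planned that would catch the first case. *Blinding* lets the treating physician break the code for a pregnancy, but that helps only once the pregnancy is known.

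**Working it through.** No formula applies and the plan states no figure to reproduce. The check is to set the sections side by side.

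**Step 1. Does the online option reach the baseline visit?** Yes. It names baseline as well as follow-up visits, and offers Zoom in place of attendance. *Exclusion criteria* has eligibility confirmed at a first appointment after the phone screen, and *Assessments at each visit* invites people to a baseline assessment after telephone screening. These appear to be the same visit. No separate in-person screening visit is described that would supply the missing checks.

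**Step 2. What does the online rule do with each check that bears on an exclusion?**

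| Baseline check | Exclusion | Online rule | Possible by video? |
|---|---|---|---|
| Physical examination | 1 | Not mentioned | No |
| Urine pregnancy test | 4 | Not mentioned | Only with a home or local test, which the plan does not provide for |
| Urine toxicology | 6 | Investigator's discretion; local collection if judged medically necessary | Not by video alone |

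The sentence on local collection follows the one on blood samples and urine toxicology, and its pronouns refer to those samples. It does not extend to the pregnancy test or the examination. Toxicology differs from the other two: the plan expressly relaxes it, so it should not be counted as a check with an assured route.

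**Step 3. Are the examination and pregnancy test still required?** Yes. The online paragraph relaxes only what it names. The baseline list, the two exclusions, the initial-visit pregnancy test and the sequence in *Study Design/Methodology* all stand.

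**Step 4. What happens if a result is missing?** The pregnancy rule in *Safety Assessments* acts on a positive test. Criterion 1 acts on history or on an abnormality found at examination. Criterion 4 acts on pregnancy itself, which has to be known to be applied. A test or examination that was not done therefore produces no finding to act on. The sequence rule puts drug after baseline measures, but does not say what counts as complete baseline measures for an online visit. *Randomization* states no hold for missing results.

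**Step 5. How many participants?** The plan gives no expected share of online baselines. The logical range is 0 to all 80, which tells the reader nothing useful. Under 1:1 allocation, about half of any affected participants would be assigned brexpiprazole. The pregnancy-test part applies only to women of childbearing years among them, a number that is also not given.

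**The case against.** The strongest reply is that the plan is silent on logistics rather than defective. The online wording is permissive and relaxes only blood samples and urine toxicology. Anything not relaxed stays mandatory, so a participant who has not had the examination or the pregnancy test is simply not yet eligible. *Ethical Considerations* also commits the study to Good Clinical Practice and the IND regulations. History and interview still cover known illness, known pregnancy, lactation and contraception.

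Much of this stands. A reader might infer that the protocol allows dosing without these checks, or that no section makes their results a condition of entry. The documents do not support that: the exclusions, the confirmation of criteria at the first appointment and the order of baseline and drug make them eligibility conditions assessed before treatment. Nor do two rules contradict each other outright. One rule leaves a gap in carrying out another.

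The reply does not close the gap. The permitted format cannot deliver the examination, and that goes beyond missing detail. The same paragraph already makes toxicology discretionary although exclusion 6 depends on it, so staff could read the silence on the other two checks either way. Routine oversight may come too late: *Monitoring Committee* schedules yearly meetings, while each participant's study lasts 13 weeks.

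Two further limits are fair. The EKG, weight and vital signs share the omission, but none decides a listed exclusion, and *Risks of Electrocardiogram* reads as if the EKG may be conditional. They add little here. Whether the pharmacy section should also state a release check is mostly a drafting choice.

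**Conclusion.** The point holds as a gap in the online rule. When baseline is on Zoom, the physical examination and the pregnancy test remain required before drug, but the plan gives no way to obtain them and does not say that their absence stops randomisation or dispensing.

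The residual risk is narrow. The pregnancy test is the stronger half, because it is planned at one time point only and interview cannot detect an unrecognised pregnancy. The examination is the weaker half, because history covers part of criterion 1.

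The conclusion rests on two readings: that the first appointment and the baseline visit are the same, and that the local-collection sentence covers only blood samples and urine toxicology. A reader might also infer that a known share of participants was exposed or harmed. The documents give no count of online baselines and no basis for such a figure. This is a cheap improvement, not a flaw that undermines the trial.

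**What to change.** Add one sentence to the online paragraph of *Assessments at each visit*. When the baseline visit is online, two items must be documented and reviewed by the investigator before randomisation and first dispensing:

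- a negative urine pregnancy test for women of childbearing years, with a home or local test acceptable;
- the baseline physical examination, done in person or by a local clinician.

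The cost is a short amendment and, for online participants, one local or in-person contact with a few days' delay. Both procedures are already in the plan, and local collection is already accepted for other samples. A matching line in *Randomization* would be tidy but is optional.
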